17.3.8. ADVERSE EVENTS LEADING TO DEATH

AEs leading to death are those AEs with “Outcome” = “Fatal” on the “Adverse Events” CRF form.

AEs leading to death will be summarized by SOC and PT.

17.3.9. ADVERSE EVENTS OF POTENTIAL DRUG ABUSE AND DEPENDENCE

AEs associated with potential drug abuse and dependence will be identified as described in [APPENDIX 5](#).

These AEs will be summarized by PT only.

17.3.10. EXTRAPYRAMIDAL ADVERSE EVENTS

Extrapyramidal AEs will be identified by MedDRA SMQ 20000095 Extrapyramidal syndrome as described in [APPENDIX 6](#).

These AEs will be summarized by PT only.

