Overall summary of the incidence of all AEs, AEs related to COVID-19, study medication-related AEs, severe AEs, serious AEs, AEs leading to discontinuation from study, AEs leading to study medication withdrawal, AEs leading to study medication interruption, and AEs leading to death will be provided by treatment group. This overall incidence summary will also be separately presented for the following subgroups: country, sex, age group, number of prior hospitalizations for treatment of schizophrenia, duration of schizophrenia, and BMI category.

Listings will be provided for all AEs, AEs related to COVID-19, study medication-related AEs, severe AEs, serious AEs, AEs leading to discontinuation from the study, AEs leading to study medication withdrawal, AEs leading to study medication interruption, AEs leading to death, AEs of potential drug abuse and dependence and extrapyramidal AEs. A listing of the pre-treatment events will also be presented. When complete event start date and complete event end date are available, duration of AEs/pre-treatment events will be calculated as: event end date – event start date + 1. Duration will be presented in data listings.

Document: PPD

Author: PPD

Version Number:

1.0

Version Date:

06MAY2024

For all summaries, each subject will be counted only once within each category (e.g., an AE type, a severity level, a relationship category, a SOC, a high level term (HLT), and a PT). If not otherwise specified, all summaries will present the number and percentage of subjects as well as the number of events. For summaries by SOC and PT, AEs will be sorted by SOC based on the internationally agreed order (see [APPENDIX 4](#)) and then by PT in decreasing frequency in the “SEP-363856 50 to 100 mg/day” column. For summaries by SOC, HLT, and PT, AEs will be sorted by SOC based on the internationally agreed order and then by HLT and PT in decreasing frequency in the “SEP-363856 50 to 100 mg/day” column.

COVID-19 related pre-treatment events related pre-treatment events and AEs will be displayed similarly as any other pre-treatment events and AEs.

Document:

PPD

Author:

PPD

Version Number:

1.0

Version Date:

06MAY2024

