APPENDIX 6. EXTRAPYRAMIDAL ADVERSE EVENTS

To ensure comprehensive and consistent selection of terminology used for analyses of extrapyramidal signs and symptoms in ongoing / planned studies of SEP-363856, MedDRA preferred terms were identified from the following source:

MedDRA version 22.0 SMQ: Extrapiramidal syndrome [20000095], Broad, including all 4 sub-SMQs (Akathisia [20000096], Dyskinesia [20000097], Dystonia [20000098], and Parkinson-like events [20000099])

Description:

All preferred terms listed in the MedDRA version 22.0 SMQ for Extrapiramidal syndrome [20000095] were included. The table below depicts the preferred terms by sub-SMQ.

Table 8: Extrapiramidal Syndrome SMQ Using MedDRA v 22.0

Akathisia		Dyskinesia		Dystonia		Parkinson-like	
PT	Code	PT	Code	PT	Code	PT	Code
Akathisia	10001540	-	-	-	-	-	-
-	-	-	-	-	-	Akinesia	10001541
-	-	Athetosis	10003620	-	-	-	-
-	-	Ballismus	10058504	-	-	-	-
-	-	-	-	-	-	Bradykinesia	10006100
-	-	Buccoglossal syndrome	10006532	-	-	-	-
-	-	Chorea	10008748	-	-	-	-
-	-	Choreoathetosis	10008754	-	-	-	-
-	-	-	-	-	-	Cogwheel rigidity	10009848
-	-	Dopamine dysregulation syndrome	10067468	-	-	-	-
-	-	-	-	Dopa-responsive dystonia	10080034	-	-
-	-	Dyskinesia	10013916	-	-	-	-
-	-	Dyskinesia neonatal	10013922	-	-	-	-
-	-	Dyskinesia oesophageal	10013924	-	-	-	-
-	-			Dystonia	10013983		
-	-			Dystonic tremor	10073210		
-	-	-	-	Early onset primary dystonia	10076668	-	-
-	-	-	-	Emprosthotonus	10014566	-	-
-	-	-	-	-	-	Freezing phenomenon	10060904
-	-	Grimacing	10061991	-	-	-	-
-	-	-	-	-	-	Hypertonia	10020852

Document: PPD

Author: PPD

Version Number:

1.0

Version Date:

06MAY2024

Akathisia		Dyskinesia		Dystonia		Parkinson-like	
PT	Code	PT	Code	PT	Code	PT	Code
-	-	-	-	-	-	Hypertonia neonatal	10048615
-	-	-	-	-	-	Hypokinetic dysarthria	10082243
-	-	-	-	Meige's syndrome	10027138		
-	-	-	-	-	-	Muscle rigidity	10028330
-	-	Oculogyric crisis	10030071	Oculogyric crisis	10030071		
-	-	-	-	-	-	On and off phenomenon	10030312
-	-	-	-	Opisthotonus	10030899	-	-
-	-			Oromandibular dystonia	10067954	-	-
-	-	-	-	-	-	Parkinsonian crisis	10048868
-	-	-	-	-	-	Parkinsonian gait	10056242
-	-	-	-	-	-	Parkinsonian rest tremor	10056437
-	-	-	-	-	-	Parkinsonism	10034010
-	-	-	-	-	-	Parkinsonism hyperpyrexia syndrome	10071243
-	-	-	-	-	-	Parkinson's disease	10061536
-	-	-	-	-	-	Parkinson's disease psychosis	10074835
-	-	Pharyngeal dyskinesia	10070912	-	-	-	-
-	-	-	-	Pharyngeal dystonia	10081226	-	-
-	-	-	-	Pleurothotonus	10035628	-	-

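### The SAP text plans no percentage of subjects with at least one extrapyramidal AE, overall or for the four sub-SMQs that Appendix 6 defines

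*SAP*

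**What the plan says.** SAP 17.3.10 (body numbering; the table of contents shows it as 17.3.8) selects the events by the whole SMQ: "Extrapyramidal AEs will be identified by MedDRA SMQ 20000095 Extrapyramidal syndrome as described in" Appendix 6. It then fixes the display: "These AEs will be summarized by PT only".

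Appendix 6 uses the broad version of the SMQ, "including all 4 sub-SMQs": akathisia, dyskinesia, dystonia and Parkinson-like events. It says of Table 8: "The table below depicts the preferred terms by sub-SMQ". Each sub-SMQ has its own column.

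SAP 17.3 names the categories of its overall incidence table, beginning "Overall summary of the incidence of all AEs, AEs related to COVID-19, study medication-related AEs, severe AEs, serious AEs" and going on to AEs leading to discontinuation, withdrawal, interruption and death. EPS AEs are not among them. The same section plans subject-level listings, among them "AEs of potential drug abuse and dependence and extrapyramidal AEs". It also sets the default content of AE tables: unless otherwise specified, "all summaries will present the number and percentage of subjects as well as the number of events", with a subject counted once within a category.

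The all-AE tables in SAP 17.3.1 are by PT, by SOC and PT, and by SOC, HLT and PT. None has an SMQ level.

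**The concern.** The safety question a reader brings to this section is how many subjects had an EPS event, and of which kind. The sponsor has defined four groups that would answer it, but the text stops at single preferred terms. A percentage per term does not convert into a percentage of subjects, so the grouped answer is left to be derived after the data are seen.

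The question matters more here than in many trials. Subjects move from antipsychotics that include strong D2/D3 binders (Protocol Appendix II) to a drug described as not acting on D2 receptors (Protocol 4.2). Their EPS medicines are tapered alongside the old antipsychotic (Protocol 10.3.4). SAS, BARS and AIMS are scheduled only at Visits 2 and 10. Between those visits they are given only if EPS needing treatment develops (Protocol Table 2, note q), and unscheduled values have no time point of their own in by-visit summaries (SAP 6.4). AE reports are therefore the main planned record of EPS while the taper is under way.

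**Working it through.** The plan gives no EPS figure to reproduce. The check has three steps.

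**1. Is a grouped incidence planned anywhere in the text?**

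| Place | Level planned | Any-EPS or sub-SMQ percentage? |
|---|---|---|
| SAP 17.3, overall summary | Named AE categories | No EPS category |
| SAP 17.3.1, all AEs | PT; SOC/PT; SOC/HLT/PT | No SMQ level |
| SAP 17.3.10, EPS AEs | PT only | Not specified |
| SAP 17.3, listings | Subject-level records | Listing, not a summary |
| SAP Appendix 6, Table 8 | Terms by sub-SMQ | Defines groups, plans no output |

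**2. How large are the groups, and do they overlap?** Appendix 6 gives no count, only that "All preferred terms listed in the MedDRA version 22.0 SMQ for Extrapiramidal syndrome [20000095] were included". Counting Table 8 column by column:

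- Akathisia 8, dyskinesia 27, dystonia 43, Parkinson-like 40. Entries: 8 + 27 + 43 + 40 = 118.
- Thirteen terms stand in more than one column. Three are in all four (Extrapyramidal disorder, Motor dysfunction, Movement disorder), one is in three (Drooling) and nine are in two.
- Surplus entries: 3 × 3 + 1 × 2 + 9 × 1 = 20.
- Distinct terms: 118 − 20 = 98.

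**3. Can the group incidence be recovered from the PT rows?** Let terms 1 to k in a group be reported by x1, …, xk subjects, each subject counted once per term. The number of distinct subjects in the group then lies between max(xi), if the same subjects report every term, and the smaller of N and the sum of the xi, if no subject reports two. The PT table fixes only these bounds.

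Assumed example: N = 101, the number enrolled in SAP 3.4, taking all of them as dosed; two terms in one group, 3 subjects each.

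- Each PT row: 3/101 = 3.0%.
- Lower bound for the group: max(3, 3)/101 = 3/101 = 3.0%.
- Upper bound for the group: (3 + 3)/101 = 6/101 = 5.9%.

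The two rows are the same in either case, while the group incidence differs by a factor of two.

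The common-AE table does not help. Its cut-off in SAP 17.3.1 is 2.0% without rounding. With N = 101, 2/101 = 1.98% falls short and 3/101 = 2.97% passes, so a term needs three subjects to appear. EPS events spread over several terms with one or two subjects each would all be absent from it.

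**The case against.** Several counter-arguments have force.

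- **Single terms do get percentages.** A reader might infer that the trial will report no percentage for akathisia, dyskinesia, dystonia or parkinsonism. The documents do not support that. Akathisia, Dyskinesia, Dystonia and Parkinsonism are preferred terms in Table 8, and by the default in SAP 17.3 each has its own n (%) if reported. Only the grouped figures are unspecified.
- **PT only may just mean no SOC level.** Neighbouring sections tabulate by SOC and PT, and AEs of potential abuse (SAP 17.3.9) use the same PT-only wording. A reader might infer that an any-EPS row is ruled out. The text neither plans nor excludes one, and the table templates to which SAP section 8 refers are not in the documents. This stands, and it limits the point to what the SAP text specifies.
- **Other outputs cover the domain.** The EPS listing together with Table 8 would allow exact group rates later. BARS, AIMS and SAS have their own summaries (SAP 17.8.2 to 17.8.4), and changes on those scales are the protocol's named movement endpoints. They also serve better than AEs to show EPS falling after the switch, since AEs are events starting at or after first dose. This stands. However, a listing is not a planned summary, the scales are scheduled at only two visits, and dystonia has no scale of its own.
- **A pooled figure from a broad SMQ is blunt.** The list includes non-specific terms such as Muscle spasms, Dysphonia and Restlessness, and one report of Movement disorder would raise all four groups. This is a good reason to keep the PT rows visible, but not a reason to omit the grouped rows.

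**Conclusion.** The gap is real but modest. The SAP defines four EPS groups and specifies no subject-level percentage for any of them or for EPS overall. The planned PT rows cannot supply these five figures.

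The size depends on how reports cluster within subjects, which the documents cannot tell us. The range of 3.0% to 5.9% is an illustration that rests on an assumed pattern of reports and on all 101 enrolled subjects having been dosed. It does not forecast EPS incidence in this trial. The count of 98 terms describes the search list; a PT table would show only terms actually reported.

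This is a cheap improvement to a safety table. It does not touch the primary or secondary endpoint. If the templates already carry the rows, the remedy is to say so in 17.3.10.

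**What to change.** In SAP 17.3.10:

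1. Report n (%) of subjects with at least one EPS AE overall and in each of the four sub-SMQs of Appendix 6, each subject counted once per row, with the PTs beneath.
2. State that a PT listed in several sub-SMQs counts in each of them, and that its subject counts once in the overall row.
3. Note that the SMQ is the broad version, so the grouped rows are to be read together with the PT rows.

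In SAP 17.3, add EPS AEs as a category of the overall AE incidence summary.

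The cost is five more rows in one table, one of them repeated in the overall summary. The groupings already exist in Appendix 6 and no new data are needed. The downside is that the grouped figures will include non-specific terms, which is why the PT rows should stay.

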17.3.11. ADVERSE EVENTS BY SUBGROUPS

The subgroup factors of interest for AE summaries include: country, sex, age group, number of prior hospitalizations for treatment of schizophrenia, duration of schizophrenia, and BMI category (see [Section 7.5](#)). AE by subgroup summaries are described in the individual sections above.

17.3.12. PSYCHIATRIC ADVERSE EVENTS LEADING TO DISCONTINUATION FROM STUDY (PAEDCs)

Additional information is collected for the non-serious psychiatric AEs that led to discontinuation from the study as well as for all serious psychiatric AEs within the study. The information is recorded in separate trackers and not part of the CRF. This information will be presented in separate data listings only.

Document:	PPD		
Author:	PPD	Version Number:	1.0

Version Date:

06MAY2024

17.4. LABORATORY EVALUATIONS

Results from the central laboratory to be reported for this study include Hematology, Chemistry (including lipid panel and thyroid panel), Urinalysis, Urine drug screening, Rapid Urine Drug Screening, Serology panel, Serum pregnancy (β -HcG) (in female subjects only), Urine pregnancy (in female subjects only), Rapid Urine Pregnancy Test (in female subjects only), Follicle stimulating hormone (FSH) (in female subjects with suspected menopause).

Serum and urine pregnancy results in female subjects, FSH level in female subjects, serology panel in subjects, and any unexpected lab parameters not specified in protocol Section 22 (APPENDIX IV. CLINICAL LABORATORY TESTS) will only be listed. Laboratory parameters prespecified in protocol Section 22 under the categories of "HEMATOLOGY", "BLOOD CHEMISTRIES" (plus HOMA-IR if collected), "URINALYSIS", and "URINE DRUG SCREENING/ RAPID URINE DRUG SCREENING" will be summarized in tables as well as presented in listings.

Listing presentations will use both standard international (SI) Units and conventional units (CV). Table summaries will also be provided using both SI units and conventional units.

Quantitative laboratory measurements reported as "< X", i.e., below the lower limit of quantification (BLQ), or "> X", i.e., above the upper limit of quantification (ULQ), will be converted to X for the purpose of quantitative summaries, but they will be presented as recorded, i.e., as "< X" or "> X" in the listings.

The following summaries will be provided:

- By-visit summary of observed values and change from Baseline values for quantitative measurements in hematology, chemistry, and urinalysis. Serum prolactin results will be summarized overall and separately by sex. Glucose, insulin and lipid panel results (total cholesterol, LDL cholesterol, HDL cholesterol and triglycerides) will be summarized by fasting status: fasting only and overall (fasting, non-fasting, or fasting status unknown combined). Change from Baseline for glucose, insulin and lipid panel results will only be calculated if post-Baseline fasting status is matching Baseline fasting status.
- By-visit summary of the number and percentage of subjects in each outcome category for qualitative measurements in urinalysis (as applicable) and for urine drug screening results. Urine drug screening results will be reported as "Positive" / "Negative".
- Shift in laboratory results (chemistry, hematology, urinalysis) from Baseline to Week 8/Visit 10 and LOCF Endpoint according to the reference range criteria. The existing reference range indicators provided by the central laboratory will be mapped as needed to categories of "Normal" (within the reference range) / "Abnormal" (outside the reference range) for urinalysis non-pH results, and to categories of "Low" (below the reference range) / "Normal" (within the reference range) / "High" (above the reference range) for chemistry and hematology results as well as urinalysis pH results.

Document: PPD

Author: PPD

Version Number:

1.0

Version Date:

06MAY2024

- Number and percentage of subjects with at least one potentially clinically significant (PCS) laboratory value (see [APPENDIX 7](#)) post Baseline. The period of evaluation includes the follow-up period, including unscheduled visits. Subjects will be counted in a particular PCS category if they met that PCS criteria at least once post Baseline, regardless of their Baseline value.

All laboratory data will be provided in data listings, with the values outside the reference ranges flagged. In addition, separate listings will be provided to present the laboratory data that met the PCS criteria.

Boxplots will be created to present Baseline and Week 8/Visit 10 values by treatment group for lipid parameters (total cholesterol, LDL, HDL, and triglycerides), glucose, insulin by fasting status: fasting only and overall (fasting, non-fasting, or fasting status unknown combined). In addition, boxplots will be created to present Baseline and Week 8/Visit 10 prolactin values by treatment group by sex: Overall, males, females. Lastly, the values of HbA1c will be presented for Baseline and Week 8/Visit 10 by treatment group in boxplots as well. Each of these boxplots will be repeated to present the change from Baseline values.

17.4.1. LABORATORY SPECIFIC DERIVATIONS

No applicable derivaitons.

17.4.2. LABORATORY REFERENCE RANGES

Laboratory reference range indicators will be provided by the laboratory vendor and used in statistical analyses. Only if a reference range indicator is missing in the data transfer will it be derived in the analysis step as described below.

- Quantitative laboratory measurements (that are not urinalysis erythrocytes or urinalysis leukocytes) will be compared with the relevant laboratory reference ranges in original units and categorized as:
 - Low: Below the lower limit of the laboratory reference range.
 - Normal: Within the laboratory reference range (upper and lower limit included).
 - High: Above the upper limit of the laboratory reference range.
- For laboratory parameters with categorical outcomes as well as urinalysis erythrocytes and urinalysis leukocytes, if the result is within the reference range, the indicator is "NORMAL"; if the result is not within range, the indicator is "ABNORMAL".

Document: PPD

Author: PPD

Version Number:

1.0

Version Date:

06MAY2024

17.5. ECG EVALUATIONS

Data from the centrally over-read ECG (Electrocardiogram) results will be included in the reporting of this study.

The following ECG parameters will be reported for this study:

- PR Interval (msec)
- RR Interval (msec)
- QRS Duration (msec)
- QRS Axis (deg)
- QT Interval (msec)
- QTcF Interval (msec) (Fridericia's Correction of QT interval)
- QTcB Interval (msec) (Bazett's Correction of QT interval)
- Heart Rate (bpm)
- Overall assessment of ECG as determined by the central over-read:
 - Normal
 - Abnormal, Insignificant
 - Abnormal, Potentially Significant
 - Abnormal, Significant
 - Exclusion Alert (only given for the Screening visit). In table summaries, the category of "Exclusion Alert" will be combined into the category of "Abnormal, Significant".
 - Not Evaluable
- ECG findings

Document: PPD

Author: PPD

Version Number:

1.0

Version Date:

06MAY2024

ECG findings will only be listed. Other ECG data will be summarized in tables as well as presented in listings.

The following summaries will be provided:

- By-visit summary of observed values and change from Baseline values for quantitative measurements.
- By-visit summary of ECG overall assessment results as determined by the central over-read ("Normal", "Abnormal, Insignificant", "Abnormal, Potentially Significant", "Abnormal, Significant", "Not Evaluable").
- Shift in ECG overall assessment as determined by the central over-read from Baseline to Week 8/Visit 10, and LOCF endpoint.
- Number and percentage of subjects who met each of the QTc interval prolongation criteria (see [Section 17.5.1](#)). The period of evaluation includes both the treatment period and the follow-up period, including unscheduled visits.
- Number and percentage of subjects with at least one PCS ECG value (see [Section 17.5.2](#)) post Baseline. The period of evaluation includes both the treatment period and the follow-up period, including unscheduled visits. Subjects will be counted in a particular PCS category if they met that PCS criteria at least once post Baseline, regardless of their Baseline value.

All ECG parameters, overall assessment as determined by the central over-read, and findings will be provided in a data listing. In addition, separate listings will be generated to present the QTc interval data of subjects who met at least one QTc prolongation criterion and the ECG data that met the PCS criteria.

17.5.1. QTc INTERVAL PROLONGATION CRITERIA

QTc interval prolongation will be identified in accordance with the following predefined criteria (same criteria apply to both QTcF and QTcB):

- > 450 msec at any post-Baseline time point (including unscheduled visits) not present at Baseline
- > 480 msec at any post-Baseline time point (including unscheduled visits) not present at Baseline
- > 500 msec at any post-Baseline time point (including unscheduled visits) not present at Baseline
- ≥ 30 msec increase from Baseline for at least one post-Baseline measurement (including unscheduled visits) and < 60 msec increase from Baseline for all post-Baseline measurements (including unscheduled visits)

Document: PPD

Author: PPD

Version Number:

1.0

Version Date:

06MAY2024

- ≥ 60 msec increase from Baseline for at least one post-Baseline measurement (including unscheduled visits)

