Fridericia's formula (QTcF) > 450 ms (males), QTcF > 470 ms (females), or PR > 220 ms. Subjects with an ECG that has a centrally overread overall interpretation of "abnormal, significant" or "abnormal, potentially clinically significant" must be discussed with the Medical Monitor. A repeat ECG for determination of eligibility may be administered once during the Screening Period and once at Baseline; requests for additional repeat ECGs must be discussed with the Medical Monitor. The repeat ECG during Screening can be conducted on a different day within the Screening Period, if needed.

- g. Subjects with known history of human immunodeficiency virus (HIV) seropositivity.
- h. Subject has type I diabetes mellitus or insulin-dependent type II diabetes.
- i. In the Investigator's judgment, the subject has current symptoms suggestive of a diagnosis of Coronavirus Disease 2019 (COVID-19), or the presence of long-term medical, neurologic, or psychiatric sequelae of prior COVID-19.

11. Subject has a history of sick sinus syndrome, second or third-degree atrioventricular (AV) block, New York Heart Association (NYHA) Class II-IV heart failure, congenital long QT syndrome, or ECG findings of myocardial ischemia/infarction or the following cardiac arrhythmias: atrial flutter or fibrillation, junctional rhythm, idioventricular rhythm, supraventricular tachycardia, ventricular tachycardia.
12. Female subject who is pregnant or lactating.
13. Subject with a supine systolic blood pressure ≥ 150 mmHg and/or supine diastolic blood pressure ≥ 95 at Screening or Baseline. A repeat blood pressure measurement is allowed once during the Screening Period and once at Baseline; requests for additional repeat blood pressure measurements for determination of eligibility must be discussed with the Medical Monitor. The repeat blood pressure measurement at Screening can be conducted on a different day within the screening period, if needed.
14. Subject has any clinically significant abnormal laboratory value(s) at Screening (hematology, chemistry, and urinalysis) as determined by the Investigator. (Note: Retesting to determine eligibility is allowed once during the Screening Period. Abnormal findings of questionable significance will be discussed with the Medical Monitor prior to including any subject.)

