15.3.5.4. ECGs

ECG analysis will be based on the centrally read data. Observed values and changes from Baseline in ECG parameters will be summarized along with shift in ECG overall assessment. In addition, the number and percentage of subjects with prolonged QTc intervals (> 450 msec, > 480 msec, and > 500 msec) and changes in QTc intervals ≥ 30 but < 60 msec and ≥ 60 msec will be summarized. Fridericia's correction (QTcF) and Bazett's correction (QTcB) will be used for QT interval correction.

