3.7. CHANGES TO ANALYSIS FROM PROTOCOL

There are no changes to analysis from the protocol.

Document:	PPD		
Author:	PPD	Version Number:	1.0

Version Date: 06MAY2024

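### SAP 17.5.1 limits the QTc >450, >480 and >500 msec counts to subjects not already above the limit at Baseline, a restriction that Protocol 15.3.5.4 lacks and SAP 3.7 does not declare

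*SAP*

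**What the plan says.** Protocol 15.3.5.4 (ECGs) plans to summarise "the number and percentage of subjects with prolonged QTc intervals (> 450 msec, > 480 msec, and > 500 msec", together with QTc changes of 30 to under 60 msec and of 60 msec or more. It uses both the Fridericia and the Bazett correction and places no condition on the Baseline value.

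SAP 17.5.1 defines the first of its three absolute criteria as "> 450 msec at any post-Baseline time point (including unscheduled visits) not present at Baseline". The 480 and 500 msec criteria carry the same restriction, and all of them apply to QTcF and QTcB. Two change-from-Baseline criteria complete the set.

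SAP 17.5 builds two outputs from these criteria. One is a table: "Number and percentage of subjects who met each of the QTc interval prolongation criteria". The other is a filtered listing: "separate listings will be generated to present the QTc interval data of subjects who met at least one QTc prolongation criterion". It also plans an unfiltered listing: "All ECG parameters, overall assessment as determined by the central over-read, and findings will be provided in a data listing". For the other ECG outliers (heart rate, PR, QRS), the same section counts subjects "if they met that PCS criteria at least once post Baseline, regardless of their Baseline value".

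SAP 3.7 states: "There are no changes to analysis from the protocol".

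At entry, Protocol 8.2 (criterion 10f) excludes a centrally read Screening ECG with "Fridericia's formula (QTcF) > 450 ms (males), QTcF > 470 ms (females), or PR > 220 ms". It gives no numeric QTcB limit.

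**The concern.** In many trials, counting only new QTc prolongation is harmless because Baseline is close to untreated. Here it is not. Baseline is the last value before the first dose (SAP 6.2), and Protocol 7.1 keeps subjects on the full dose of the pre-switch antipsychotic when SEP-363856 starts. Protocol 4.1 names QTc prolongation among the side effects of some atypical agents. A QTc that was long on the old drug and stays long after the switch is a result that a switch study should be able to report as a frequency. The restriction removes those persisting values from the row for that limit.

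At stake is one descriptive safety table and its listing. The percentages in that table can only be equal to or lower than those the protocol's plain reading would give, and nothing in the SAP tells a reader that the definition was narrowed.

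**Working it through.** The plan states no figure to reproduce, so the check sets the two rules side by side and applies them to example values.

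**Inputs.** Limits of 450, 480 and 500 msec (Protocol 15.3.5.4; SAP 17.5.1). Change bands of 30 to under 60 and 60 or more msec (both documents). Screening QTcF limits of 450 msec for men and 470 msec for women (Protocol 8.2). 101 subjects enrolled (SAP 3.4).

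**Rules.** Let B be the Baseline QTc and P a post-Baseline QTc.
- Protocol, plain reading: count at limit L if P > L.
- SAP: count at limit L if P > L and B ≤ L. Count in a change band if 30 ≤ P − B < 60 for the largest rise, or if P − B ≥ 60.

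**Applied to hypothetical pairs** (absolute limits for the protocol; all five criteria for the SAP):

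| B → P (msec) | Rise | Protocol limits met | SAP criteria met |
|---|---|---|---|
| 440 → 455 | 15 | >450 | >450 |
| 455 → 455 | 0 | >450 | none |
| 455 → 480 | 25 | >450 | none |
| 455 → 484 | 29 | >450, >480 | >480 |
| 455 → 485 | 30 | >450, >480 | >480 and 30 to <60 |
| 485 → 490 | 5 | >450, >480 | none |
| 485 → 505 | 20 | >450, >480, >500 | >500 |
| 505 → 510 | 5 | >450, >480, >500 | none |

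Two results follow.

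1. Whenever B > L and P > L, the subject is missing from the SAP row for L, whatever the size of the rise.
2. The subject is missing from every SAP row, and so from the dedicated QTc listing, only if two further conditions hold: P − B < 30, and no higher limit is newly crossed. For B between 451 and 480 this means P between 451 and 480 with a rise of at most 29 (whole msec).

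**Can such subjects be in the study?** Yes. The SAP limit of 450 is the same for both sexes, while women with a Screening QTcF of 451 to 470 are eligible. The numeric limits are tied to the Screening ECG, so a Day 1 value can lie higher. QTcB has no numeric limit. For QTcF the effect falls mainly in the >450 row.

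**Size per case.** If all 101 enrolled subjects form the denominator, each omitted subject lowers a row by 1/101 = 0.99%, about 1 percentage point.

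**Denominator.** SAP 17 bases safety outcomes on the safety population, and 17.5.1 names no other denominator. The new-onset percentages would therefore include subjects who were above the limit at Baseline and cannot qualify.

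**The case against.** The best defence is that the protocol sentence is brief. It fixes no time point, does not say how Baseline or unscheduled values enter, and does not literally say that every subject above a limit is counted. Protocol 15 leaves statistical detail to the SAP, so 17.5.1 could be read as supplying that detail by defining treatment-emergent prolongation, which is a legitimate summary in a single-arm study. This stands in part: the new-onset count deserves to be kept. But an unrestricted count is the plainer reading of the protocol, the SAP gives no reason for narrowing it, and its own neighbouring ECG table ignores the Baseline value.

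The second defence is that little is hidden. Large worsening still reaches the table and listing through a rise of 30 msec or more or a newly crossed limit. All ECG values are listed, by-visit summaries show observed QTc and change, a shift table covers the overall ECG assessment, and investigators record clinically significant ECG changes as adverse events. This also stands. What is missing is the tabulated frequency above each limit, which none of those outputs gives.

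Third, an unrestricted count does not by itself isolate the effect of SEP-363856. The only scheduled post-Baseline ECG is at Week 8 or early termination, and a subject who leaves early may still be on the old drug, because the taper can run to Week 6. That is a fair caution about interpretation. It does not justify omitting the count.

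**Conclusion.** The point holds as an undeclared difference between protocol and SAP in one descriptive safety table. It does not touch the primary or secondary endpoint. Subjects above a QTc limit both at Baseline and afterwards are not counted in that limit's row; a subset is also absent from every QTc category and from the QTc listing.

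Three stronger readings are tempting and are not supported.
- A reader might infer that anyone with a long QTc before and after the switch disappears from the QTc outputs. That happens only when the rise is under 30 msec and no higher limit is newly crossed.
- A reader might infer that the values go unreported. They stay in the full ECG listing and the by-visit summaries.
- A reader might want to state what share of the study is affected. The documents give neither the sex split nor the distribution of Baseline QTc, so any such figure would rest on invented inputs. It would also be a ceiling if it counted all women with Baseline QTcF of 451 to 470, because those whose QTc falls to 450 or below are uncounted under either rule.

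The supportable size is about 1 percentage point per omitted subject in a row, assuming a denominator of 101. The conclusion rests on the plain reading of Protocol 15.3.5.4 and on the SAP's condition meaning that the subject was not above the same limit at Baseline.

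**What to change.** In SAP 17.5.1, for each of the three limits and for both QTcF and QTcB:

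- Add the number and percentage of subjects above the limit at any post-Baseline time, regardless of Baseline. This is the protocol's analysis. Show the Baseline count beside it.
- Keep the present count as an additional row labelled as new onset. Its denominator should be subjects at or below the limit at Baseline who have a post-Baseline ECG.
- Extend the dedicated QTc listing in SAP 17.5 to everyone in the unrestricted count, as well as those meeting a change criterion.
- Record the new-onset restriction in SAP 3.7 as an addition to the protocol's analysis.

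The Baseline count and the new-onset denominator go beyond what the protocol asks for, but without them neither percentage can be interpreted. No new data are needed. The cost is a few extra table rows, a wider listing filter, and QTc percentages that may look slightly less favourable.
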